#### 14.2 Clinical Laboratory Evaluation

Results for clinical laboratory parameters (serum chemistry and hematology), vital signs, ECGs, and physical examinations will be summarized by cohort and combined and by study visits.

Descriptive summary statistics in observed values as well as changes from baseline will be

presented. In addition, thresholds of marked laboratory abnormalities based on NCI CTCAE v5.0 will be summarized by worst grade shift from baseline (see Appendix B).

Table 7 shows clinical laboratory assessments (hematology, chemistry, and urinalysis) that were performed performed. Chemistry and hematology laboratory parameters will be summarized by cohort and scheduled visit. Urinalysis assessments will be listed but not summarized due to their qualitative nature.

**Table 7** Clinical Laboratory Parameters

Chem	istry	Hematology	Urinalysis
Sodium	Creatinine	Hematocrit	Specific gravity
Potassium	Total Bilirubin	Hemoglobin	Protein
Chloride	AST/SGOT	WBC count	Glucose
Bicarbonate	ALT/SGPT	Neutrophils	Ketones
Calcium	<del>ALP</del> ‡	Lymphocytes	Urobilinogen
Magnesium	Albumin	Monocytes	Occult blood
Phosphorous	Total protein	Eosinophils	Microscopic sediment
			evaluation ‡
Glucose		Basophils	
Blood urea nitrogen		Platelet count	WOCBP only:
			β-HCG§

ALT = alanine aminotransferase; ALP = alkaline phosphatase; AST = aspartate aminotransferase; HCG = β-human chorionic gonadotropin pregnancy; SGOT = serum glutamic-oxaloacetic transaminase; SGPT = serum glutamic pyruvic transaminase; WBC = white blood count; WOCBP = women of child-bearing potential

Numeric results will be summarized using (6-point) descriptive statistics at baseline and at each scheduled post-baseline time point, unless otherwise specified. Changes from baseline will also be summarized by scheduled time point, where available. Selected laboratory results will be listed with CTCAE reference ranges.

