104         Chemistry         Phosphorous         mg/dL         2.5         5           104         Chemistry         Potassium         mmol/L         3.5         5.1           104         Chemistry         Sodium         mmol/L         136         145           104         Chemistry         Total Bilirubin         mg/dL         0         1.4	104	Chemistry	Glucose			mg/dL	85	125
104         Chemistry         Potassium         mmol/L         3.5         5.1           104         Chemistry         Sodium         mmol/L         136         145           104         Chemistry         Total Bilirubin         mg/dL         0         1.4	104	Chemistry	Magnesium			mg/dL	1.9	2.7
104         Chemistry         Sodium         mmol/L         136         145           104         Chemistry         Total Bilirubin         mg/dL         0         1.4	104	Chemistry	Phosphorous			mg/dL	2.5	5
104 Chemistry Total Bilirubin mg/dL 0 1.4	104	Chemistry	Potassium			mmol/L	3.5	5.1
	104	Chemistry	Sodium			mmol/L	136	145
	104	Chemistry	Total Bilirubin			mg/dL	0	1.4
104 Chemistry Total protein g/dL 6 8.3	104	Chemistry	Total protein			g/dL	6	8.3

SITE	DANIEL	D / D / 14557777	CENT	. 65	III III G	REFERENCE	REFERENCE
NUMBER	PANEL	PARAMETER	SEX	AGE	UNITS	LOW	HIGH
104	Hematology	Basophils			THOUS/MCL	0	0.2
104	Hematology	Eosinophils			THOUS/MCL	0	0.5
104	Hematology	Hematocrit			%	39.5	50
104	Hematology	Hemoglobin			g/dL	13.5	16.9
104	Hematology	Lymphocytes			THOUS/MCL	0.9	3.3
104	Hematology	Monocytes			THOUS/MCL	0	0.8
104	Hematology	Neutrophils			THOUS/MCL	2	8.1
104	Hematology	Platelet count			THOUS/MCL	150	400
104	Hematology	WBC count			THOUS/MCL	4	10.5
104	Urinalysis	Glucose			mg/dL	Negative	
104	Urinalysis	Ketones			mg/dL	Negative	
104	Urinalysis	Occult blood			/HPF	2	
104	Urinalysis	Protein			mg/dL	Negative	
104	Urinalysis	Specific gravity				1.003	1.03
104	Urinalysis	Urobilinogen			mg/dL	< 2	

Table 12 Site 105 Units and Reference Ranges by Parameter

SITE NUMBER	PANEL	PARAMETER	SEX	AGE	UNITS	REFERENCE LOW	REFERENCE HIGH
105	Chemistry	Sodium			mEq/L	135	145
105	Chemistry	Potassium			mEq/L	3.6	5.2
105	Chemistry	Chloride			mEq/L	98	108
105	Chemistry	Bicarbonate			mEq/L	22	32
105	Chemistry	Calcium			mg/dL	8.9	10.2
105	Chemistry	Phosphorous			mg/dL	2.5	4.5
105	Chemistry	Magnesium			mg/dL	1.8	2.4
105	Chemistry	Blood urea nitrogen			mg/dL	8	21
105	Chemistry	Albumin			g/dL	3.5	5.2
105	Chemistry	ALP			U/L		

SITE NUMBER	PANEL	PARAMETER	SEX	AGE	UNITS	REFERENCE LOW	REFERENCE HIGH

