105	Chemistry	ALT/SGPT	M	0 -< 50	U/L	10	64
105	Chemistry	ALT/SGPT	M	50 - high	U/L	10	48
105	Chemistry	ALT/SGPT	F		U/L	7	33
105	Chemistry	AST/SGOT			U/L	9	38
105	Chemistry	Creatinine	M		mg/dL	0.51	1.18
105	Chemistry	Creatinine	F		mg/dL	0.38	1.02
105	Chemistry	Glucose			mg/dL	62	125
105	Chemistry	Total Bilirubin			mg/dL	0.2	1.3
105	Chemistry	Total protein			g/dL	6	8.2
105	Hematology	Hematocrit	M		%	38	50
105	Hematology	Hematocrit	F		%	36	45
105	Hematology	Hemoglobin	M		g/dL	13	18
105	Hematology	Hemoglobin	F		g/dL	11.5	15.5
105	Hematology	Neutrophils			thou/uL	1.8	7
105	Hematology	Lymphocytes			thou/uL	1	4.8
105	Hematology	Monocytes			thou/uL	0	0.8
105	Hematology	Eosinophils			thou/uL	0	0.5
105	Hematology	Basophils			thou/uL	1.8	7
105	Hematology	Platelet count			thou/uL	150	400
105	Hematology	WBC count			x10^3/uL	20	1000
105	Urinalysis	Glucose				Negative	
105	Urinalysis	Ketones				Negative*	
105	Urinalysis	Occult blood				1.005	1.03
105	Urinalysis	Protein				negative	
105	Urinalysis	Specific gravity					
105	Urinalysis	Urobilinogen				negative	

 Table 13
 Site 107 Units and Reference Ranges by Parameter

SITE						REFERENCE	REFERENCE
NUMBER	PANEL	PARAMETER	SEX	AGE	UNITS	LOW	HIGH
107	Chemistry	Albumin			g/L	38	50
107	Chemistry	ALP			U/L	40	150
107	Chemistry	ALT/SGPT			U/L	7	40
107	Chemistry	AST/SGOT			U/L	5	34
107	Chemistry	Bicarbonate			mmol/L	23	29

SITE NUMBER	PANEL	PARAMETER	SEX	AGE	UNITS	REFERENCE LOW	REFER HIC	
107	Chemistry	Blood urea nitrogen			mmol/L	2.5*		7.1*
107	Chemistry	Calcium			mmol/L	2.2		2.62
107	Chemistry	Chloride			mmol/L	100		110
107	Chemistry	Creatinine	M		μmol/L	64		110
107	Chemistry	Creatinine	F		μmol/L	50		98
107	Chemistry	Glucose			mmol/L	3.8		7
107	Chemistry	Magnesium			mmol/L	0.7		1.1
107	Chemistry	Phosphorous			mmol/L	0.81*		1.4*
107	Chemistry	Potassium			mmol/L	3.2		5
107	Chemistry	Sodium			mmol/L	135		145
107	Chemistry	Total Bilirubin			μmol/L	low	< 23	
107	Chemistry	Total protein			g/L	65		80
107	Hematology	Hematocrit			L/L	0.42		0.54
107	Hematology	Hematocrit			L/L	0.33		0.47
107	Hematology	Hemoglobin	M		g/L	140		180
107	Hematology	Hemoglobin	F		g/L	120		160
107	Hematology	Neutrophils			10^9/L	2		7.5
107	Hematology	Lymphocytes			10^9/L	1.5		4
107	Hematology	Monocytes			10^9/L	0.2		0.8
107	Hematology	Eosinophils			10^9/L	0.04		0.4
107	Hematology	Basophils			10^9/L	0		0.2
107	Hematology	Platelet count			10^9/L	150		400
107	Hematology	WBC count			10^9/L	4		11
107	Urinalysis	Glucose				Negative		

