107	Urinalysis	Ketones				Negative		
107	Urinalysis	Occult blood				Negative	Trace	
107	Urinalysis	Protein				Negative	Trace	
107	Urinalysis	Specific gravity				1.005		1.03
107	Urinalysis	Urobilinogen			umol/L	low	< 17	

Table 14 Site 110 Units and Reference Ranges by Parameter

SITE				-		REFERENCE	REFERENCE
NUMBER	PANEL	PARAMETER	SEX	AGE	UNITS	LOW	HIGH
110	Chemistry	Albumin			g/L	39	50
110	Chemistry	ALP	M		U/L	42	110
110	Chemistry	ALP	F		U/L	32	93

SITE NUMBER	PANEL	PARAMETER	SEX	AGE	UNITS	REFERENCE LOW	REFERENCE HIGH
110	Chemistry	ALP	F		U/L	47	124
110	Chemistry	ALT/SGPT	M		U/L	8	58
110	Chemistry	ALT/SGPT	F	16 - 50	U/L	7	36
110	Chemistry	ALT/SGPT	F	51 - high	U/L	8	45
110	Chemistry	AST/SGOT	M		U/L	15	38
110	Chemistry	AST/SGOT	F	16 - 50	U/L	14	30
110	Chemistry	AST/SGOT	F	51 - high	U/L	15	37
110	Chemistry	Bicarbonate			mmol/L	21	31
110	Chemistry	Blood urea nitrogen	M	16 - 30	mmol/L	2.5	6.3
110	Chemistry	Blood urea nitrogen	M	31 - 40	mmol/L	3.1	8
110	Chemistry	Blood urea nitrogen	M	41 - 50	mmol/L	3.6	7.8
110	Chemistry	Blood urea nitrogen	M	50 - high	mmol/L	3	8.8
110	Chemistry	Blood urea nitrogen	F	16 - 40	mmol/L	2.5	6.4
110	Chemistry	Blood urea nitrogen	F	41 - 50	mmol/L	2.8	6.7
110	Chemistry	Blood urea nitrogen	F	50 - high	mmol/L	2.9	8
110	Chemistry	Calcium		16 -< 59	mmol/L	2.11	2.55
110	Chemistry	Calcium		59 - high	mmol/L	2.24	2.63
110	Chemistry	Chloride			mmol/L	100	109
110	Chemistry	Creatinine	M		umol/L	67	109
110	Chemistry	Creatinine	F		umol/L	49	882
110	Chemistry	Glucose			mmol/L	3.6*	5.3*
110	Chemistry	Magnesium			mmol/L	0.66	1.07
110	Chemistry	Phosphorous			mmol/L	0.88	1.45
110	Chemistry	Potassium			mmol/L	3.6	5
110	Chemistry	Sodium			mmol/L	136	148
110	Chemistry	Total Bilirubin			umol/L	4	23
110	Chemistry	Total protein			g/L	67	87
110	Hematology	Hematocrit	M			0.395	0.488
110	Hematology	Hematocrit	F			0.347	0.449

SITE			~===	. ~=		REFERENCE	REFERENCE
NUMBER	PANEL	PARAMETER	SEX	AGE	UNITS	LOW	HIGH
110	Hematology	Hemoglobin	M		g/dL	13.3	17.1
110	Hematology	Hemoglobin	F		g/dL	11.5	14.8
110	Hematology	Neutrophils			x10^9/L	2.01	7.42
110	Hematology	Lymphocytes			x10^9/L	1.06	3.61
110	Hematology	Monocytes			x10^9/L	0.26	0.85
110	Hematology	Eosinophils			x10^9/L	0.02	0.45
110	Hematology	Basophils			x10^9/L	0.02	0.09
110	Hematology	Platelet count			x10^9/L	167	396
110	Hematology	WBC count			x10^9/L	3.89	9.93
110	Urinalysis	Glucose			mg/dL	Negative	
110	Urinalysis	Ketones			mg/dL	Negative	
110	Urinalysis	Occult blood				Negative	

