113	Chemistry	Blood urea nitrogen	SLIX	90 - high	mg/dL	10	
113	Chemistry	Calcium		Ü	mg/dL	4.5	5.6
113	Chemistry	Chloride			mmol/L	97	106
113	Chemistry	Creatinine			mg/dL	0.76	1.27
113	Chemistry	Creatinine			mg/dL	0.57	1
113	Chemistry	Glucose			ng/mL	65	199
113	Chemistry	Magnesium			mg/dL	1.6	2.3
113	Chemistry	Phosphorous			mg/dL	2.5	4.5
113	Chemistry	Potassium			mmol/L	3.5	5.2
113	Chemistry	Sodium			mmol/L	134	144
113	Chemistry	Total Bilirubin			mg/dL	0	1.2
113	Chemistry	Total protein			g/dL	6	8.5
113	Hematology	Hematocrit			%	43.5	53.7
113	Hematology	Hemoglobin			g/dL	14.1	18.1
113	Hematology	Neutrophils			x10E3/uL	1.4	. 7
113	Hematology	Lymphocytes			x10E3/uL	0.7	3.1
113	Hematology	Monocytes			x10E3/uL	0.1	0.9
113	Hematology	Eosinophils			x10E3/uL	0	0.4
113	Hematology	Basophils			x10E3/uL	0	0.2
113	Hematology	Platelet count			x10E3/uL	150	450
113	Hematology	WBC count			x10E3/uL	3.4	10.8
113	Urinalysis	Glucose				Negative	
113	Urinalysis	Ketones				Negative	
113	Urinalysis	Occult blood				Negative	
113	Urinalysis	Protein				Negative	
113	Urinalysis	Specific gravity				1	1.035
113	Urinalysis	Urobilinogen				Normal	

Table 17 Site 116 Units and Reference Ranges by Parameter

SITE			Ü	·		REFERENCE	REFERENCE
NUMBER	PANEL	PARAMETER	SEX	AGE	UNITS	LOW	HIGH
116	Chemistry	Albumin		20 - 60	g/L	35	52
116	Chemistry	Albumin		61 - 90	g/L	32	46
116	Chemistry	ALP			U/L	40	150
116	Chemistry	ALT/SGPT			U/L	< 56	

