#### Rain Therapeutics Inc. RAIN-701 SAP

SITE NUMBER	PANEL	PARAMETER	SEX	AGE	UNITS	REFERENCE LOW	REFERENCE HIGH
116	Chemistry	AST/SGOT			U/L	5	34
116	Chemistry	Bicarbonate			mmol/L	22	29
116	Chemistry	Blood urea nitrogen	M		mmol/L	3.2	7.4
116	Chemistry	Blood urea nitrogen	F		mmol/L	2.5	6.7
116	Chemistry	Calcium			mmol/L	2.1	2.55
116	Chemistry	Chloride			mmol/L	98	107
116	Chemistry	Creatinine	M		umol/L	63.6	110.5
116	Chemistry	Creatinine	F		umol/L	50.4	98.1
116	Chemistry	Glucose			mmol/L	3.6*	5.3*
116	Chemistry	Magnesium			mmol/L	0.66	1.07
116	Chemistry	Phosphorous			mmol/L	0.74	1.52
116	Chemistry	Potassium			mmol/L	3.5	5.1
116	Chemistry	Sodium			mmol/L	136	145
116	Chemistry	Total Bilirubin			umol/L	5.1	20.5
116	Chemistry	Total protein			g/L	64	83
116	Hematology	Hematocrit		M	%	37	52
116	Hematology	Hematocrit		F	%	35	47
116	Hematology	Hemoglobin		M	g/dL	12.5	17.5
116	Hematology	Hemoglobin		F	g/dL	11.5	16
116	Hematology	Neutrophils			K/uL	1.7	88
116	Hematology	Lymphocytes			K/uL	1	4.5
116	Hematology	Monocytes			K/uL	0.2	1
116	Hematology	Eosinophils			K/uL	0	0.5
116	Hematology	Basophils			K/uL	0	0.2
116	Hematology	Platelet count			K/uL	150	400
116	Hematology	WBC count			× 109/L	3.54*	9.06*
116	Urinalysis	Glucose				Negative	
116	Urinalysis	Ketones				Negative	
116	Urinalysis	Occult blood				Negative	
116	Urinalysis	Protein				Negative	
116	Urinalysis	Specific gravity				1.001	1.035
116	Urinalysis	Urobilinogen					

 Table 18 Site 117 Units and Reference Ranges by Parameter

SITE		DADAMETED	C	·		REFERENCE	REFERENCE
NUMBER 117	PANEL Chemistry	PARAMETER Albumin	SEX	AGE 18 -	g/dL	LOW 3.7	HIGH 4.8
117	Chemistry	Albuilliii		59	g/uL	3.7	4.0
117	Chemistry	Albumin		60 - 89	g/dL	3.2	4.6
117	Chemistry	Albumin		90 - high	g/dL	2.9	4.5
117	Chemistry	ALP		15 - 20	IU/L	50	180
117	Chemistry	ALP		20 - high	IU/L	40	140
117	Chemistry	ALT/SGPT				7*	41*
117	Chemistry	AST/SGOT				12*	38*
117	Chemistry	Bicarbonate			meq/L	22*	30*
117	Chemistry	Blood urea nitrogen			mg/dL	10	25
117	Chemistry	Calcium			mg/dL	8.6	10.4
117	Chemistry	Chloride			mmol/L	98	111
117	Chemistry	Creatinine	M		mg/dL	< 1.28	
117	Chemistry	Creatinine	F		mg/dL	< 1.16	
117	Chemistry	Glucose			mg/dL	50	140
117	Chemistry	Magnesium			mg/dL	1.8	2.3
117	Chemistry	Phosphorous			mg/dL	2.5	4.5
117	Chemistry	Potassium			mmol/L	3.5	5
117	Chemistry	Sodium			mmol/L	135	145
117	Chemistry	Total Bilirubin			mg/dL	< 1.2	
117	Chemistry	Total protein			g/dL	6	8.3
117	Hematology	Hematocrit	M		%	41	53

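### SAP Appendix A has erroneous or incomplete limits for creatinine, glucose and hemoglobin at Sites 104, 110 and 113, which can misgrade subjects in the CTCAE shift tables

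*SAP*

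**What the plan says.** SAP Section 15 discloses that units and reference ranges for the local laboratories were not collected. The sponsor assigned them from available information and a textbook; the result is Appendix A. The documents name no other source of laboratory limits.

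Section 14.2 says that marked laboratory abnormalities under CTCAE v5.0 "will be summarized by worst grade shift from baseline (see Appendix B"). Appendix B grades creatinine, glucose (as hypoglycemia) and hemoglobin (as anemia), and each Grade 1 definition uses the site's upper or lower limit of normal.

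The rows at issue in Appendix A are:

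- Table 14, Site 110: "Creatinine F umol/L 49 882". The male row in the same table is 67 to 109 umol/L.
- Table 16, Site 113: "Glucose ng/mL 65 199".
- Table 11, Site 104: "Hemoglobin g/dL 13.5 16.9", with no sex given.
- Table 16, Site 113: "Hemoglobin g/dL 14.1 18.1", with no sex given.
- Table 16, Site 113: two creatinine ranges, 0.76 to 1.27 and 0.57 to 1 mg/dL, with no sex given.

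Both unsexed hemoglobin rows stand in tables that split other analytes by sex: albumin and creatinine at Site 104, ALT at Site 113.

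**The concern.** Section 4 gives the SAP two tasks: a full safety analysis and a summary of the available efficacy data. Laboratory toxicity is read from the shift tables, and the limits behind them come from Appendix A alone, so an error in a graded row passes straight into a reported grade. The possible errors run in different directions: creatinine under-graded, anemia over-graded at Grade 1, and hypoglycemia over-graded if the unit label is honoured.

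Other rows suggest that the appendix was not checked line by line. Site 105 has "WBC count x10^3/uL 20 1000" and "Basophils thou/uL 1.8 7", the latter identical to that site's neutrophil row. Site 116 has "Neutrophils K/uL 1.7 88". These matter less. Appendix B has no row for white cell count or basophils, and it grades neutrophils only through the lower limit, so they affect listing flags at most.

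**Working it through.** A tabulated limit cannot be re-derived, so there is no plan figure to reproduce. The check compares each row with the other site tables and applies the Appendix B rules. Unit conversions: 1 mg/dL creatinine = 88.4 umol/L; 1 mg/dL = 10,000 ng/mL.

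**1. Creatinine, women, Site 110.** Female upper limits elsewhere, in umol/L: Site 101 91.9 (1.04 × 88.4), Sites 102 and 122 79.6 (0.9 × 88.4), Site 104 106.1 (1.2 × 88.4), Site 105 90.2 (1.02 × 88.4), Site 107 98, Site 116 98.1, Site 117 102.5 (1.16 × 88.4). The printed 882 is 882 / 88.4 = 9.98 mg/dL. Ratios: 882 / 106.1 = 8.3 to 882 / 79.6 = 11.1; against men at the same site, 882 / 109 = 8.1.

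Appendix B grades on the upper limit (ULN): Grade 1 above ULN, Grade 2 above 1.5 × ULN, Grade 3 above 3 × ULN, Grade 4 above 6 × ULN. Grades 2 and 3 are also met above 1.5 and 3.0 times baseline. The documents do not give the correct limit. I assume a range from 88.2 (a lost decimal point) to 98.1 (Site 116).

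| ULN (umol/L) | Grade 1 above | Grade 2 above | Grade 3 above | Grade 4 above |
|---|---|---|---|---|
| 882 (printed) | 882 | 1323 | 2646 | 5292 |
| 88.2 | 88.2 | 132.3 | 264.6 | 529.2 |
| 98.1 | 98.1 | 147.2 | 294.3 | 588.6 |

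Three illustrations:

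- Baseline 70, value 104: the baseline rule needs more than 1.5 × 70 = 105. Grade 0 with 882; Grade 1 with 88.2 or 98.1.
- Baseline 110, value 160: the baseline rule needs more than 1.5 × 110 = 165. Grade 0 with 882; Grade 2 with 88.2 or 98.1. Protocol Section 5.1 admits creatinine clearance down to 30 mL/min, so a raised baseline is possible.
- Baseline 70, value 120: 120 exceeds 105, so Grade 2 under all three limits.

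**2. Glucose, Site 113.** As labelled, 65 to 199 ng/mL is 0.0065 to 0.0199 mg/dL. A recorded value of 100 converts to 100 / 10,000 = 0.01 mg/dL, below the Grade 4 cut point of 30 mg/dL. If the number is read as mg/dL, the lower limit of 65 equals that at Sites 101, 102 and 103 and no grade changes. Sites 107, 110 and 116 use mmol/L and most others mg/dL, so any pooled glucose summary needs a unit conversion.

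**3. Hemoglobin, Sites 104 and 113.** Female lower limits at sites with a female row run from 11.0 (Site 101) to 12.1 g/dL (Site 102). The band in which a woman would wrongly be Grade 1 is:

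- Site 104: 13.5 − 12.1 = 1.4 to 13.5 − 11.0 = 2.5 g/dL.
- Site 113: 14.1 − 12.1 = 2.0 to 14.1 − 11.0 = 3.1 g/dL.

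The limit also grades the baseline value, so the shift can go wrong in more than one way. At Site 104, against an assumed female limit of 11.6 (as at Sites 103 and 111):

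| Baseline → worst (g/dL) | Shift with 13.5 | Shift with 11.6 |
|---|---|---|
| 13.6 → 12.5 | 0 to 1 | 0 to 0 |
| 13.0 → 12.5 | 1 to 1 | 0 to 0 |
| 12.5 → 11.0 | 1 to 1 | 0 to 1 |

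Grades 2 and 3 use the absolute cut points of 10.0 and 8.0 g/dL and do not move.

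**4. Creatinine, Site 113.** Without a sex key, Grade 1 starts above 1.27 or above 1.0 mg/dL, and ULN-based Grade 2 above 1.5 × 1.27 = 1.905 or 1.5 × 1.0 = 1.5 mg/dL. A value of 1.1 is Grade 0 or Grade 1 depending on the row chosen.

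**Scale.** Tables are by cohort and overall; Section 10.3 rules out analyses by center. SAP Table 1 gives 41 subjects: 11, 22 and 8 in Cohorts A, B and C. One misgraded subject is 1/41 = 2.4% overall and 1/8 = 12.5% of Cohort C.

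**The case against.** The strongest reply is that nothing here shows a wrong table. The documents give no enrollment by site and sex. If no woman was treated at Sites 104, 110 or 113, the female creatinine and hemoglobin problems have no effect. The glucose problem needs a program that converts ng/mL literally. The value 882 may be 88.2 with a decimal point lost when the PDF is read as text. The SAP also discloses openly that the limits were assigned.

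Much of this stands. A reader might infer that the shift tables are wrong at these sites, but there are no tables by site and no evidence of who was affected. A reader might also infer that creatinine toxicity in Site 110 women is concealed. That goes too far, because the baseline multiples still catch Grades 2 and 3 in women with a normal baseline. Nor are the hemoglobin limits impossible: both ranges are ordinary, Site 102 men have 14.3 to 18.1 g/dL, and the fault is a missing female row. No share of women affected can be stated, since the documents give no hemoglobin distribution.

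The rest does not stand. A lost decimal cannot explain the ng/mL label, the missing female rows or the unkeyed creatinine ranges. Disclosing where limits came from does not validate each row.

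**Conclusion.** The concern holds in limited form. Appendix A is the stated source of units and limits, and its rows for creatinine (Sites 110 and 113), glucose (Site 113) and hemoglobin (Sites 104 and 113) are erroneous or incomplete as printed. Followed literally, they can misgrade subjects in the pooled shift tables as follows.

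- **Creatinine, Site 110 women:** Grade 1 and ULN-based Grade 4 practically unreachable; Grades 2 and 3 reachable only through the baseline multiples.
- **Glucose, Site 113:** Grade 4 if converted as labelled; no change if read as mg/dL.
- **Hemoglobin, women at Sites 104 and 113:** false Grade 1 anemia at baseline or later; Grades 2 and 3 unaffected.
- **Creatinine, Site 113:** limit not assignable without a sex key.

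The actual effect rests on three things the documents leave open: whether women were treated at Sites 104, 110 and 113, how the program handles units, and whether 882 is what the original page shows. If that page reads 88.2, the Site 110 item falls away and the others remain. This should be corrected, but it is not evidence that a reported result is wrong.

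**What to change.** Before the shift tables are run (or before they are relied on, if already run):

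1. Check the Site 110 female creatinine limit on the original SAP page, then against the site laboratory record, and correct it if needed.
2. Correct the Site 113 glucose unit.
3. Assign sex to the two Site 113 creatinine rows.
4. Add sex-specific hemoglobin limits at Sites 104 and 113. Where no site record exists, use the textbook range and mark it with the asterisk that Appendix A already uses.
5. Verify every other Appendix A row for an analyte graded in Appendix B against the site laboratory record.
6. In the same pass, correct rows that affect only listing flags, such as Site 105 white cell count and basophils and the Site 116 neutrophil upper limit.

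An automatic screen for large fold-differences between sites is no substitute. The hemoglobin limits differ from a female limit of 11.6 by only 13.5 / 11.6 = 1.16 and 14.1 / 11.6 = 1.22, and such a screen would also miss the unkeyed creatinine rows.

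The cost is a revision of the SAP appendix, a line-by-line check, and a rerun of any tables already produced. No new patient data are needed.

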#### Rain Therapeutics Inc. RAIN-701 SAP

SITE NUMBER	PANEL	PARAMETER	SEX	AGE	UNITS	REFERENCE LOW	REFERENCE HIGH
116	Chemistry	AST/SGOT			U/L	5	34
116	Chemistry	Bicarbonate			mmol/L	22	29
116	Chemistry	Blood urea nitrogen	M		mmol/L	3.2	7.4
116	Chemistry	Blood urea nitrogen	F		mmol/L	2.5	6.7
116	Chemistry	Calcium			mmol/L	2.1	2.55
116	Chemistry	Chloride			mmol/L	98	107
116	Chemistry	Creatinine	M		umol/L	63.6	110.5
116	Chemistry	Creatinine	F		umol/L	50.4	98.1
116	Chemistry	Glucose			mmol/L	3.6*	5.3*
116	Chemistry	Magnesium			mmol/L	0.66	1.07
116	Chemistry	Phosphorous			mmol/L	0.74	1.52
116	Chemistry	Potassium			mmol/L	3.5	5.1
116	Chemistry	Sodium			mmol/L	136	145
116	Chemistry	Total Bilirubin			umol/L	5.1	20.5
116	Chemistry	Total protein			g/L	64	83
116	Hematology	Hematocrit		M	%	37	52
116	Hematology	Hematocrit		F	%	35	47
116	Hematology	Hemoglobin		M	g/dL	12.5	17.5
116	Hematology	Hemoglobin		F	g/dL	11.5	16
116	Hematology	Neutrophils			K/uL	1.7	88
116	Hematology	Lymphocytes			K/uL	1	4.5
116	Hematology	Monocytes			K/uL	0.2	1
116	Hematology	Eosinophils			K/uL	0	0.5
116	Hematology	Basophils			K/uL	0	0.2
116	Hematology	Platelet count			K/uL	150	400
116	Hematology	WBC count			× 109/L	3.54*	9.06*
116	Urinalysis	Glucose				Negative	
116	Urinalysis	Ketones				Negative	
116	Urinalysis	Occult blood				Negative	
116	Urinalysis	Protein				Negative	
116	Urinalysis	Specific gravity				1.001	1.035
116	Urinalysis	Urobilinogen					

 Table 18 Site 117 Units and Reference Ranges by Parameter

SITE		DADAMETED	C	·		REFERENCE	REFERENCE
NUMBER 117	PANEL Chemistry	PARAMETER Albumin	SEX	AGE 18 -	g/dL	LOW 3.7	HIGH 4.8
117	Chemistry	Albuilliii		59	g/uL	3.7	4.0
117	Chemistry	Albumin		60 - 89	g/dL	3.2	4.6
117	Chemistry	Albumin		90 - high	g/dL	2.9	4.5
117	Chemistry	ALP		15 - 20	IU/L	50	180
117	Chemistry	ALP		20 - high	IU/L	40	140
117	Chemistry	ALT/SGPT				7*	41*
117	Chemistry	AST/SGOT				12*	38*
117	Chemistry	Bicarbonate			meq/L	22*	30*
117	Chemistry	Blood urea nitrogen			mg/dL	10	25
117	Chemistry	Calcium			mg/dL	8.6	10.4
117	Chemistry	Chloride			mmol/L	98	111
117	Chemistry	Creatinine	M		mg/dL	< 1.28	
117	Chemistry	Creatinine	F		mg/dL	< 1.16	
117	Chemistry	Glucose			mg/dL	50	140
117	Chemistry	Magnesium			mg/dL	1.8	2.3
117	Chemistry	Phosphorous			mg/dL	2.5	4.5
117	Chemistry	Potassium			mmol/L	3.5	5
117	Chemistry	Sodium			mmol/L	135	145
117	Chemistry	Total Bilirubin			mg/dL	< 1.2	
117	Chemistry	Total protein			g/dL	6	8.3
117	Hematology	Hematocrit	M		%	41	53
117	Hematology	Hematocrit	F		%	36	46
117	Hematology	Hemoglobin	M		g/dL	13.5	17
117	Hematology	Hemoglobin	F		g/dL	12	15
117	Hematology	Neutrophils			K/uL	1.8	7.7
117	Hematology	Lymphocytes			K/uL	1.1	4
117	Hematology	Monocytes			K/uL	0	0.8
117	Hematology	Eosinophils			K/uL	0	0.7
117	Hematology	Basophils			K/uL	0	0.2
117	Hematology	Platelet count			K/uL	150	450
117	Hematology	WBC count			K/uL	3.8	10.6

SITE						REFERENCE	REFERENCE
NUMBER	PANEL	PARAMETER	SEX	AGE	UNITS	LOW	HIGH
117	Urinalysis	Glucose				Negative	
117	Urinalysis	Ketones				Negative	
117	Urinalysis	Occult blood				Negative	
117	Urinalysis	Protein				Negative	
117	Urinalysis	Specific gravity				1.005	1.03
117	Urinalysis	Urobilinogen			U/dL	< 2.0	

